1. DEFINITIONS OF ADVERSE EVENTS

1.1 Adverse Event (AE)

An adverse event is any untoward medical occurrence in a patient or clinical investigation subject administered a pharmaceutical product that does not necessarily have a causal relationship with this treatment. An adverse event can therefore be any unfavourable and unintended sign including an abnormal laboratory (or vital sign, ECG, etc.) finding, symptom or disease temporally associated with the use of an investigational medicinal product (IMP). All adverse events, whether or not considered by the Investigator to be related to the IMP (test product, comparator or placebo), must be described and recorded on the appropriate Adverse Event forms in the CRF. Where possible, a diagnosis should be made. Anticipated fluctuations of pre-existing conditions, including the disease under study that do not represent a clinically significant exacerbation or worsening need not be considered AEs.

Clinical Laboratory and Other Adverse Events

If a laboratory result is considered by the investigator to be clinically significant or have a clinically significant pathological change from baseline it should be recorded as an AE.

Other abnormal results (e.g. x-rays, scans, physical examination findings) that worsen from baseline and/or are considered clinically significant should also be recorded as AEs.

The investigator will exercise his or her medical and scientific judgment in deciding whether an abnormal laboratory finding or other abnormal assessment is clinically significant.

AEs should be reported and documented in accordance with the procedures outlined below. All AEs occurring during the study must be documented on the relevant CRF/e-CRF pages. The following data should be documented for each AE:

- Description of the symptom event
- Classification of 'serious' or 'not serious'
- Severity
- Date of first occurrence and date of resolution (if applicable)
- Action taken
- Causal relationship
- Outcome of event (unknown, recovered, not yet recovered, recovered with sequelae, death [with date and cause reported])

Pregnancy

Subjects will be instructed that known or suspected pregnancy occurring during the study should be reported to the investigator. The investigator should also be notified of pregnancy occurring during the study but confirmed after completion of the study. If a subject is found to be pregnant after inclusion in the study, the subject must be withdrawn from the study. Any pregnancy will be followed to term and the status of mother and child will be reported to the Sponsor after delivery.

Full details of any pregnancy will be recorded on the AE page of the CRF/eCRF, and a Pregnancy Report Form will be completed. A copy of the Pregnancy Report Form must be completed and faxed to the appropriate contact (as detailed in the Safety Management Plan) within 24 hours.

1.2 Adverse Drug Reaction (ADR)

All noxious and unintended responses to a medicinal product related to any dose administered. The phrase 'response to a medicinal product' means that a causal relationship between a medicinal product and an adverse event is at least a reasonable possibility.

1.3 Serious Adverse Event (SAE) or Drug Reaction

A Serious Adverse Event or reaction is any untoward medical occurrence that at any dose:

- results in death,
- is life-threatening (patient at risk of death at time of event; not hypothetically life-threatening),
- requires inpatient hospitalisation or prolongation of existing hospitalisation,
- results in persistent or significant disability or incapacity,
- is a congenital anomaly or birth defect,
- is an important medical event (see below for definition).

The term "life-threatening" in the definition of "serious" refers to an event in which the patient was at risk of death at the time of the event; it does not refer to an event which hypothetically might have caused death if it were more severe.

Medical and scientific judgement must be exercised in deciding whether expedited reporting is appropriate in other situations, such as important medical events that may not be immediately life-threatening or result in death or hospitalisation but may jeopardise the patient or may require intervention to prevent one of the other outcomes listed in the definition above. These should also usually be considered serious.

Examples of such events are intensive treatment in an emergency room or at home for allergic bronchospasm; blood dyscrasias or convulsions that do not result in hospitalisation; or development of drug dependency or drug abuse.

The following medical conditions will be automatically regarded as serious, regardless of the classification assigned by the clinical trial Investigator reporting the case:

- Anaphylaxis or anaphylactoid reaction
- Myocardial infarction
- Stroke
- Pulmonary embolism
- Infection with any blood borne virus
- Any transmissible spongiform encephalopathy
- Development of inhibitors to IMP

In general, information that might materially affect the risk-benefit assessment of a medicinal product or that would suggest changes in the way it is to be administered or to the way a clinical investigation should be conducted should be reported in an expedited manner. Examples include:

- Single case reports of an expected adverse reaction with an unexpected outcome e.g. fatal outcome
- For an expected serious adverse reaction, an increase in the rate of occurrence which is judged to be clinically important.
- A significant hazard to the patient population, such as lack of efficacy in treating life-threatening diseases or an event which is significant enough to lead to important changes in the way a medicine is developed e.g. change in dose, monitoring, consent forms.
- A major new safety finding from a newly completed animal study.
- A serious adverse event associated with a study procedure that could modify the conduct of the trial.

1.4 Unexpected ADRs

An adverse reaction, the nature or severity of which is not consistent with the applicable product information (e.g. Investigator's Brochure for an unapproved investigational product or summary of product characteristics (SmPC) for an authorised product). Reports which add significant information on specificity, severity or frequency about a listed ADR would be classed as 'unexpected', for example, a report of interstitial nephritis when acute renal failure is the listed ADR or a report of fulminant hepatitis when the product information only lists hepatitis.

Expectedness will be assessed against the SmPC.

1.5 Suspected Unexpected Serious Adverse Reactions (SUSARs)

All suspected adverse reactions related to an IMP (the tested IMP, comparators or placebo) which occur that are both unexpected and serious (SUSARs) are subject to expedited reporting. BPL and/or the Designated CRO (as stated in the Safety Management Plan) will be responsible for reporting these to the concerned competent authorities and to the Ethics Committee concerned, as detailed in the Safety Management Plan.

2. DETECTING ADVERSE EVENTS

Subjects will be carefully monitored for adverse events that occur after the Informed Consent Form (ICF) has been signed until the last day of the study. The Investigator or delegate will question the subjects about adverse events using a non-leading question such as "How are you feeling?" The Investigator will also record adverse events reported spontaneously by the subjects. Clinically significant changes in the findings of physical examination, and clinically significant abnormalities in the result of objective tests (e.g. laboratory variables, ECG) may also be recorded as AEs. The Investigator will use the following criteria when deciding whether to report an abnormal result as an adverse event:

- 1. The test result is associated with accompanying symptoms.
- 2. Results of additional diagnostic tests cause concern or necessitate medical intervention.
- 3. As a consequence of the test result, the dose administered to the subject is changed, the subject is withdrawn, or the subject is given concomitant treatment.
- 4. The Investigator considers the result to constitute an AE.

If any of the above criteria are met, the Investigator will report the results as an AE.

2.1 Causality

All AEs will be recorded in the CRF/e-CRF, whether considered to be related or unrelated to the treatment. The record will include the following: brief description of event (preferably a diagnosis), date and time started and stopped, severity, outcome, actions taken and classification of the AE. The Investigator should also evaluate the probability of

CONFIDENTIAL

Page 63 of 100

a causal relationship of the AE to the study medication according to the following criteria as:

1. Unrelated – Clinical event with an incompatible time relationship to IMP administration, or that could be explained by underlying disease or other drugs or chemicals, or is incontrovertibly not related to the IMP.

2. Unlikely - Clinical event whose time relationship to IMP administration makes a causal connection improbable, but that could plausibly be explained by underlying disease or other drugs or chemicals.

3. Possible - Clinical event with a reasonable time relationship to IMP administration, but that could also be explained by concurrent disease or other drugs or chemicals.

4. Probable - Clinical event with a reasonable time relationship to IMP administration, and is unlikely to be attributed to concurrent disease or other drugs or chemicals.

5. Very likely / certain – Clinical event with plausible time relationship to IMP administration, and that cannot be explained by concurrent disease or other drugs or chemicals.

Study medication is defined as those investigational compounds or their controls used in a study.

It will be assumed that for all adverse events classified as "probably related", "possibly related" or "very likely / certainly related" to the study medication, there is reasonable likelihood that the adverse event was causally related to the product. All such adverse events will be regarded as "causally related" to the study medication.

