10.7.1 Adverse Events

Adverse events (AEs) will be coded by the MedDRA (Medical Dictionary for Regulatory Authorities) system organ class and preferred term. Only treatment emergent AEs (*ie* beginning after dosing with Optivate[®]) will be included in the summary tables. All AEs (CRF and study diary) will be included in the data listings.

A bleed will not be reported as an adverse event, unless it represents a consistent worsening of FVIII deficiency symptoms or the subject is hospitalised. Bleed details will be recorded in the study diary by the subject. However, any excessive bleeding as a result of the surgery will be recorded as an adverse event.

Any complications of surgery that meet the definitions of a Serious Adverse Event (see Appendix I) will be reported as a Serious Adverse Events.

Adverse Drug Reactions (ADRs) will be defined as AEs which are recorded as having a possible, probable or very likely/certain causality related to Optivate[®]. If the Investigator cannot assign severity or causality as described in Appendix I, BPL will class the event as related. AEs leading to withdrawal will be defined as events where the Optivate[®] was discontinued as a result of the AE.

The denominator used for the calculation of percentages will be the number of subjects in the safety population. For all AE summaries described below, counting will be performed by subjects and event. For counts by subject, subjects experiencing the same event more than once will have that event counted only once within each system organ class and once within each preferred term.

The following summaries of treatment-emergent AEs will be provided:

Summary of AEs

All the AE data (from CRF and study diary) will be pooled together and reported in terms of the type, duration, treatment and/or severity.

The number and percentage of subjects reporting AEs, serious AEs (SAEs), ADRs, AEs leading to withdrawal and AEs leading to death. The number of AEs, SAEs, ADRs, AEs leading to withdrawal and SAEs leading to death.

Summary of AEs by Severity of Event

The number and percentage of subjects reporting AEs and ADRs, will be summarised by system organ class and by preferred term. The severity of event will be recorded once per subject for each preferred term as the maximum severity experienced by each subject (*ie* where the order of most severe to least severe is given by: severe, moderate then mild).

Summary of AEs by Causality

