10.2. ADVERSE EVENTS

Adverse events will be coded to system organ classes and preferred terms using MedDRA version 16.1.

Treatment emergent AEs are defined as events that have onset following the first infusions of Optivate®, or events present before the first infusion of Optivate®, but which worsen in severity following the first infusion of Optivate®. Should the time of onset be missing, but the date of onset be equal to the date of first dosing with Optivate®, then it will be assumed such events are treatment emergent.

Should the day of onset be missing, for the purposes of assigning treatment emergence, the day will be taken to be 01, unless the month and year are the same as the month and year of first infusion of Optivate[®], in which case the date of first infusion of Optivate[®] will be taken.

Should the day and month be missing, for the purposes of assigning treatment emergence, the day and month will be taken to be 01 January, unless the year is the same as the year of first infusion of Optivate®, in which case the date of first infusion of Optivate® will be taken.

All adverse events will be listed, however only treatment emergent adverse events will be included in the summary tables.

Sponsor: BPL

Protocol: 8VWF07

Version: 1.0

Statistical Analysis Plan

Where severity or causality is missing for an event, for the purposes of the tables, these will be assumed to be severe and very likely/certain respectively. Similarly, where severity or causality changes during the course of the event, the worst case will be taken for the analysis.

Summary tables presenting frequency of AEs by SOC and PT will be ordered by overall descending frequency of SOC and then, within a SOC, by overall descending frequency of PT.

The following tables of adverse events will be produced:

- An overall summary of the number and percentage of subjects reporting TEAEs, serious TEAEs, treatment related TEAEs, TEAEs leading to withdrawal and TEAEs leading to death
- TEAEs overall and by system organ class and preferred term
- Study treatment related TEAEs overall and by system organ class and preferred term. Study-treatment related events are those recorded as having a possible, probable, or very likely/certain causality related to Optivate®.
- TEAEs by maximum severity, overall and by system organ class and preferred term
- Serious TEAEs, overall and by system organ class and preferred term

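### The *Unrelated* and *Possible* causality definitions overlap, so one event can be counted as an ADR or left out of the ADR and treatment-related counts

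*Protocol*

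**What the plan says.** Protocol Appendix I 2.1 (Causality) gives five categories. The three lowest matter here.

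- *Unrelated*: timing incompatible with administration, "or that could be explained by underlying disease or other drugs or chemicals, or is incontrovertibly not related to the IMP".
- *Unlikely*: timing that "makes a causal connection improbable, but that could plausibly be explained by underlying disease or other drugs or chemicals".
- *Possible*: "Clinical event with a reasonable time relationship to IMP administration, but that could also be explained by concurrent disease or other drugs or chemicals".

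The same section treats *Possible*, *Probable* and *Very likely / certain* as causally related. Protocol 10.7.1 makes the same cut: "Adverse Drug Reactions (ADRs) will be defined as AEs which are recorded as having a possible, probable or very likely/certain causality". SAP 5.3 repeats it for the safety endpoints, and SAP 10.2 applies it to the tables: "Study-treatment related events are those recorded as having a possible, probable, or very likely/certain causality related to" the product.

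Three conservative defaults exist. Protocol 10.7.1 has the sponsor class an event as related if the investigator cannot assign severity or causality. SAP 10.2 sets missing causality to the highest category. SAP 10.2 also takes the worst case when causality changes during an event.

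**The concern.** A causality scale used to define ADRs needs categories that do not overlap across the ADR cut. Here the middle alternative of *Unrelated* asks only that some other explanation could exist, and *Possible* also allows for another explanation. Two investigators could follow the text correctly and label the same event on opposite sides of the cut.

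Tolerability through adverse events is a secondary objective (Protocol 3), and serious ADRs are a named safety endpoint (SAP 5.3). The treatment-related and related-serious TEAE tables (SAP 10.2) rest on this label. So do two reporting routes in Protocol Appendix I: SUSARs (1.5 and 4), and SAEs with onset more than 28 days after the last dose, which are reportable only if judged at least possibly related (4).

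**Working it through.** The plan gives no figure to reproduce. The check is a comparison of the definitions, followed by simple arithmetic for scale.

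**Step 1: which categories fit.** Cross timing with the availability of another explanation, reading each definition as written and leaving aside events that are incontrovertibly not related.

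| Timing | Other explanation | Categories that fit | Side of the ADR cut |
|---|---|---|---|
| Incompatible | Any | *Unrelated* (first alternative) | Not ADR |
| Improbable | Could explain it | *Unlikely* and *Unrelated* (middle alternative) | Both not ADR |
| Reasonable | Could explain it | *Possible* and *Unrelated* (middle alternative) | **One ADR, one not** |
| Reasonable | Unlikely to account for it | *Probable* | ADR |
| Plausible | Cannot explain it | *Very likely / certain* | ADR |

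The second row is an overlap that changes no ADR count. The third row is the problem.

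**Step 2: does the wording separate the two?** *Unrelated* refers to underlying disease and *Possible* to concurrent disease. Even if those terms were meant to differ, both definitions name other drugs or chemicals in the same words, so the overlap remains for that class of explanation.

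**Step 3: does a default resolve it?** No. The three defaults cover causality that cannot be assigned, is missing, or changes over time. None applies when the investigator picks one of two fitting labels. The per-subject rules (most likely relationship in Protocol 10.7.1, worst case in SAP 10.2) operate across a subject's events after each has been labelled.

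**Step 4: what moves.** With *Unrelated* chosen, the event leaves the ADR and treatment-related counts, including Tables 14.3.1.4 and 14.3.1.5 and the treatment-related line of the overall summary. It remains in the AE listing. If treatment-emergent, it also remains in the all-TEAE and severity tables, in the serious TEAE table if serious, and in the by-relationship table under the unrelated heading.

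**Step 5: scale.** The denominator is the safety population (Protocol 10.7.1), and enrolment is planned at up to 12 (Protocol Synopsis). For one subject whose only candidate ADR is relabelled, the change is 100 × 1/N percentage points:

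- N = 12: 100/12 = 8.3 points.
- N = 10 (an assumption, since 10 is the evaluable minimum and not the safety denominator): 100/10 = 10.0 points.

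If replacements take the number treated above 12, the change is below 8.3 points.

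**The case against.** The strongest defence is that the five categories form an ordered scale and an experienced investigator will read them that way. On that reading, *Possible* describes competing causes, and *Unrelated* describes an event for which the alternative fully accounts. The defaults also lean against the product, safety analysis is descriptive, and the main product risks have their own routes: inhibitor results and serology changes are notified whatever the causality label. This limits the consequence. It does not supply a rule, because the text asks only whether another explanation could exist.

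Four stronger readings are tempting, and the documents do not support them.

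- *The event disappears.* It does not; only the related counts change.
- *A serious unexpected event would go unreported as a SUSAR.* Appendix I 4 ties one expedited route to the investigator's opinion of relatedness, so the risk is real. However, Appendix I 1.5 refers handling to a Safety Management Plan that is not available here. SAEs from consent to 28 days after the last dose reach the sponsor or CRO whatever their causality.
- *These subjects nearly always have a disease or drug explanation, so tolerability is biased.* No figure supports this. Protocol 8.2.1 and 10.7.1 keep most bleeds and expected fluctuations out of AE reporting, so many disease-explained events never reach the scale. Choosing the middle alternative over *Possible* can only take events out of the ADR count, but the amount is unknown.
- *The clause contradicts the ADR definition in Appendix I 1.2*, which requires that "a causal relationship between a medicinal product and an adverse event is at least a reasonable possibility". The closing paragraph of 2.1 applies that threshold by counting *Possible* and above as related. This is loose drafting of one category, not opposed policy.

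It is also fair that 8.3 points is the weight of any single subject in a study this size and does not measure this defect.

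**Conclusion.** The concern holds as a classification defect. An event with reasonable timing and a possible alternative explanation satisfies two definitions on opposite sides of the ADR cut, and neither the protocol nor the SAP says which prevails. The ADR, treatment-related and related-serious counts can therefore depend on which label is chosen. Relatedness-dependent reporting (SUSARs, and SAEs with onset beyond 28 days) can be affected too. All-TEAE reporting, SAE reporting up to 28 days and the primary inhibitor endpoint are untouched.

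The size is 8.3 percentage points per relabelled subject if 12 are treated, assuming the event is that subject's only candidate ADR. No misclassification rate can be derived from the documents. The conclusion assumes that no separate document, such as a CRF completion guide, already sets a precedence rule. It is worth correcting because the edit is small and the affected tables address a stated objective.

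**What to change.** In Protocol Appendix I 2.1, do one of the following:

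- delete the middle alternative of *Unrelated*, leaving incompatible timing or incontrovertibly not related; or
- join it to the first with 'and', giving incompatible timing and another explanation, or incontrovertibly not related.

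Deletion is the cleaner choice. The 'and' version would leave an event with incompatible timing and no other explanation dependent on the last alternative.

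Then add two sentences. First, an event with reasonable timing and a possible alternative explanation is *Possible* unless it is incontrovertibly not related. Second, in any other case where two categories fit, the more related one applies. Carry the same wording to the CRF guide. SAP 5.3 and 10.2 need no change, since they already cut at *Possible*.

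The cost is that some more events will count as ADRs. The number is unknown and may not be trivial: with infusions three times a week, many intercurrent events will have reasonable timing. The *incontrovertibly not related* alternative keeps clearly extraneous events out. One gap exists now and is not created by this change: improbable timing with no other explanation fits no category, and the same edit could close it.
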